## 2.6 Risks/Benefits of Roxadustat Treatment

MDS has a high disease burden without effective medical treatment. RBC transfusion is an unattractive last resort being used to support MDS patients with severe anemia. There is an urgent need to develop an effective, safe, and convenient therapy for addressing anemia in lower risk MDS.

The primary benefit of roxadustat is the correction of anemia thus the reduction of RBC transfusions. This will result in the relief of the associated anemia signs and symptoms, the avoidance of the risks associated with RBC transfusions, and an improved quality of life for these elderly patients. Roxadustat is expected to overcome the inhibitory effect of inflammation of chronic disease on erythropoiesis, to improve erythropoietic progenitor cells' response to erythropoietin, to facilitate the mobilization of iron and ultimately lead to improved erythropoiesis.

A dose adjustment algorithm will be used during the Treatment Period to minimize transfusion burden with the primary goal of reaching transfusion independence, ([Appendix C](#) and [Appendix D](#)). The risk of excessive erythropoiesis (an increase in Hb of 2.0 g/dL at any time during the treatment period) will be mitigated by use of the dose adjustment algorithm. The

erythropoietic effects of roxadustat are reversible when treatment stops. Based on the clinical and nonclinical trial results to date, it is anticipated that orally administered roxadustat will be effective in the treatment of anemia in patients with MDS who have no approved treatment with an acceptable safety profile.

## 2.7 Objectives

### 2.7.1 Primary Objective

The primary objective of this study is to evaluate the efficacy of roxadustat in the treatment of anemia in patients with lower risk MDS who have a low burden of RBC transfusion.

### 2.7.2 Secondary Objectives

The secondary objectives in this study are to:

- Evaluate the safety of roxadustat
- Evaluate the impact of roxadustat on RBC transfusion requirements
- Evaluate pharmacokinetics (PK) and pharmacodynamics (PD) of roxadustat in MDS patients
- Evaluate effect of roxadustat on quality of life parameters

### 2.7.3 Open-Label Component Objective

- Optimize the starting dose for the DB component

## 2.8 Efficacy Endpoints

### 2.8.1 Primary Efficacy Endpoint:

The primary efficacy endpoint is the proportion of patients who achieved TI  $\geq 56$  consecutive days in the first 28 weeks of treatment.

### 2.8.2 Secondary Efficacy Endpoints

- Proportion of patients who achieved  $\geq 50\%$  reduction in number of RBC transfusion over any 8 weeks compared to their baseline
- Cumulative number of patient-exposure-week of TI
- Cumulative number of pRBC packs transfused
- Proportion of patients who achieved TI for  $\geq 20$  weeks (140 days)
- Mean change from baseline in Physical Function as measured by Patient Reported Outcomes Measurement Information System (PROMIS)
- Mean change from baseline in PROMIS Fatigue score.
- Mean change from baseline in EuroQol Quality of Life Five Dimensional Five Level Health Questionnaire (EQ-5D-5L) assessment

### 2.8.3 Exploratory Endpoints

- Duration of transfusion independence
- Proportion of patients who achieve a mean Hb increase of  $\geq 1.0$  g/dL and  $\geq 1.5$  g/dL (averaged over 8 weeks in those achieved TI) compared to pre-transfusion Hb at baseline

- Impact of baseline endogenous erythropoietin levels on roxadustat treatment response and dose requirement
- Effect on hepcidin and iron indices metabolism
- Effect on cholesterol and lipid parameters

## **2.9 Safety Assessments**

Study-specific safety will be assessed by evaluating the following over 52 weeks:

[figure not shown]
- AE and SAE reporting
- N (%) of patients with progression to AML
- Clinical laboratory measures, including Hb and LFTs (AST, ALT, TBili and ALP)
- Heart rate, blood pressure, and ECG changes (including changes from Baseline)
- Evaluation of PK/PD data

### 3 STUDY DESIGN

#### 3.1 Description of the Study

The study design is illustrated in [Figure 3](#) below:

**Figure 3 Study Schemas**

Up to 24 patients will be enrolled in sequential dose level cohorts prior to start of the DB component of the study. All patients will receive roxadustat in an OL manner. The first 8 patients will receive a starting dose of 1.5 mg/kg (Dose Level 1). The next 8 patients will receive a starting dose of 2.0 mg/kg (Dose Level 2). The last 8 patients will receive a starting dose of 2.5 mg/kg (Dose Level 3). Each patient's starting dose will be determined by their actual weight at the registration/randomization visit. The roxadustat dose per body weight are estimates only and the exact dose will be assigned per body weight ranges as shown in the body of the protocol.

The OL component is intended to optimize the starting dose for the subsequent double-blind component of the study in which 160 eligible lower risk MDS patients with LTB will be randomized 3:2 to roxadustat or matching placebo. It is anticipated that the starting dose level

will be level 2 (2.0 mg/kg) and the protocol is written to reflect this but if the OL data suggests a lower (1.5 mg/kg) or a higher (2.5 mg/kg) dose to be a more optimal starting dose, then this will be implemented accordingly.

Patients in the DB component of the study will be randomized with the following stratifications:

- Serum EPO level: either  $\leq 200$  mIU/mL OR  $> 200$  mIU/mL and  $\leq 400$  mIU/mL
- IPSS-R low risk / very low risk vs. intermediate risk group classification
- RBC transfusion burden: 1 pRBC/8-weeks over 16 consecutive weeks vs 2-4 pRBC/8-weeks

For the OL and the DB components, dose adjustments/escalations will occur every 8 weeks at pre-defined dose level increments, with the exception that the starting dose will be maintained if an erythroid response (defined as a 50% reduction in pRBC from baseline) is seen after the initial 8 weeks of dosing. A re-assessment will be done for these patients at week 12 and if transfusion independence (TI) is observed the dose will not be increased. If TI is NOT observed at this point, the dose will be increased by one dose level. See [Appendix C](#) for details on dosing and dose adjustment.

Once transfusion independence for at least 8 continuous weeks has been achieved and the “maintenance treatment period” starts, the study drug dose should follow guidance described in [Appendix D](#).

When all the randomized patients complete 28 weeks of treatment or are discontinued from study medication before this time, the analysis of the primary and secondary efficacy endpoints will be performed. Only Sponsor personnel who are not directly involved with the study sites/patients will have access to the unblinded data. The blind will be maintained for study patients, PI, site staff and site monitoring personnel for the remainder of the study (to Week 52 plus a 4 week follow-up period).

The initial OL component with up to 24 patients who receive roxadustat may remain in the study up to 52 weeks of treatment based on investigator discretion, adequate safety, and impression of benefit. These patients will undergo all procedures as will the randomized patients with the exception of not completing the Health-related quality of life (HRQoL) questionnaires.

During the course of the study, visits and assessments will be performed as defined in the schedule of assessments (see [Appendix A](#) and [Appendix B](#)).

### 3.1.1 Screening Period

All screening procedures are to be completed within 28 days prior to Day 1 of Treatment, except for documentation of the following which can be obtained from patient medical records:

1. Lower risk MDS (IPSS-R very low risk, lower risk, or intermediate risk) must be documented prior to Day 1 of Treatment. There is no minimum time from diagnosis to registration/randomization except to allow for proper IPSS-R classification to be made, and to show transfusion dependence for patients in both portions of the study.
2. Results from bone marrow examination and cytogenetic analysis performed within 16 weeks prior to Day 1 of treatment can be used. The required bone marrow slides and report must be available for a centralized review at any time throughout the study.

3. Patients are deemed to have low RBC transfusion burden (LTB) if they received 1 to 4 pRBC documented transfusion within 8 weeks prior to registration/randomization. Patients with 1 pRBC/8-weeks must have a documented history of requiring 1pRBC/ 8-weeks in 2 consecutive periods of 8 weeks in the 16 weeks preceding registration/randomization. Pre-transfusion and post-transfusion Hb levels within 8 weeks prior to Day 1 of treatment will also be recorded. The percentage of patients requiring 1 pRBC transfusion at baseline will be capped at 30% for the DB portion of the study. For OL patients only, the requirement to demonstrate transfusion dependence can also be met by a PI starting this particular patient on pRBC transfusion during the screening period

All patients must meet all inclusion and have none of the exclusion criteria to be eligible to receive study medication.

### **3.1.2 Treatment Period**

The treatment duration is 52 weeks.

### **3.1.3 Follow-Up Period**

All patients who complete 52 weeks (of treatment with study medication) will undergo a 4 week follow-up period after the last dose of study medication.

Patients who discontinue study medication early (for any reason) will remain in the study through the entire 52 week study period. Patients will have a 4 week follow-up visit after stopping study medication and then be followed up at a reduced visit schedule of every 8 weeks after the final follow-up visit until the end of the study.

## **3.2 Replacement of Patients**

Patients who drop out prematurely will not be replaced in the study.

## **3.3 Study Treatment**

### **3.3.1 Dose and Schedule**

Up to 24 patients will be enrolled in sequential dose level cohorts PRIOR to start of the DB component of the study. All patients will receive roxadustat in an OL manner. The first 8 patients will receive a starting dose of 1.5 mg/kg (Dose Level 1). The next 8 patients will receive a starting dose of 2.0 mg/kg (Dose Level 2). The last 8 patients will receive a starting dose of 2.5 mg/kg (Dose Level 3). All doses will be determined by actual patient weight on registration/randomization day.

The starting dosing table for the OL portion of the study is shown below.

Dose Level Group	Approximate Roxadustat Dose (mg/kg)	Patient Weight		
		45 to <70 kg	70 - 100 kg	> 100 kg
1	1.5	70 mg TIW	120 mg TIW	150 mg TIW
2	2.0	100 mg TIW	150 mg TIW	200 mg TIW
3	2.5	150 mg TIW	200 mg TIW	250 mg TIW

The OL is intended to optimize the starting dose for the subsequent DB component of the study in which 160 eligible lower risk MDS patients with LTB will be randomized 3:2 to roxadustat or matching placebo. It is anticipated that the starting dose level will be level 2 (2.0 mg/kg) and the protocol is written to reflect this but if the OL data identifies level 1 or 3 as a more optimal starting dose, then this will be implemented.

Patients in the DB component of the study will be randomized at an overall ratio of 3:2 roxadustat or placebo with the following stratifications:

- Serum EPO level: either  $\leq 200$  mIU/mL OR  $> 200$  mIU/mL and  $\leq 400$  mIU/mL
- IPSS-R low risk / very low risk vs. intermediate risk group classification
- RBC transfusion burden: 1pRBC/8-weeks over 16 consecutive wks vs 2-4 pRBC/8wks

### 3.3.2 Dose Adjustment

There are two periods for the study drug dosing – the correction phase and the maintenance phase.

**Correction phase:** Dose adjustments/escalations will occur every 8 weeks at pre-defined dose level increments, with the exception that starting dose will be maintained if erythroid response (defined as a 50% reduction in pRBC from baseline) is seen after the initial 8 weeks of dosing. A re-assessment will be done for these patients at week 12 and if transfusion independence (TI) is observed the dose will not be increased. If TI is NOT observed at this point, the dose will be increased by one dose level (see [Appendix C](#)).

**Maintenance Phase:** Once transfusion independence for at least 8 continuous weeks ( $\geq 56$  consecutive days) has been achieved and the “maintenance treatment period” starts, the study drug dose may be escalated or reduced in pre-defined levels as described in [Appendix D](#).

During the course of the study, visits and assessments will be performed as defined in the schedule of assessments (see [Appendix A](#)).

Dose reductions can occur at any time per defined criteria (see [Appendix C](#) and [Appendix D](#)).

Dosing with study medication may be held (not given) for one single instance not to exceed 2 weeks. Please contact the medical monitor with any questions.

Given the complexities of the dose adjustment algorithm, and the need to take into consideration various clinical parameters, it is not considered a protocol deviation when study subjects are dosed based on their clinical circumstance, whether or not this is concordant with the roxadustat

dosing algorithm, unless it is related to “excessive hematopoiesis” or “Overdose” (prescribed 400 mg or > 3.5 mg/kg/dose).

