Study Design Overview (cont.):	
standard site transfusion criteria will be documented in overall study files.
 
For all patients (OL and DB components), dose adjustments/escalations will occur every 8 weeks at pre-defined dose level increments, with the exception that the starting dose will be maintained if an erythroid response (defined as a 50% reduction in pRBC transfusion from baseline) is seen after the initial 8 weeks of dosing. A re-assessment will be done for these patients at week 12 and if transfusion independence (TI) is observed the dose will not be increased. If TI is NOT observed at this point, the dose will be increased by one dose level. See Appendix C for details on dosing and dose escalation.
 
Once TI for at least 8 continuous weeks has been achieved, Maintenance Phase will begin and the study drug dose should follow guidance described in Appendix D.
 
During the course of the study, visits and assessments will be performed as defined in the schedule of assessments (see Appendix A and Appendix B).
 
The overall study duration is 52 weeks with primary efficacy assessment after the first 28 weeks in the DB component, and continued treatment up to 52 weeks.
 
The OL portion patients who receive roxadustat may remain in the study up to 52 weeks of treatment based on investigator discretion, adequate safety, and impression of benefit. These patients will undergo all procedures as the randomized patients in the DB study with the exception of not completing the Health-related quality of life (HRQoL) questionnaires.
 
When all the randomized (DB) patients complete 28 weeks of treatment or are discontinued from study medication before this time, the analysis of the primary and secondary efficacy endpoints will occur. Only Sponsor personnel who are not directly involved with the study sites/patients will have access to the unblinded data. The blind will be maintained for study patients, PI, site staff and site monitoring personnel for the remainder of the study (to Week 52 plus a 4 week follow-up period).
 
Follow-Up:
 
All patients who complete 52 weeks (of treatment with study medication) will undergo a 4 week follow-up period after the last dose of study medication.
 
Patients who discontinue study medication early (for any reason) will remain in the study through the entire 52 week study period. Patients will have a 4 week follow-up visit after stopping study medication and then be followed up at a reduced visit schedule of every 8 weeks

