## 2.5 Roxadustat Dose Rationale

For the treatment of anemia in MDS patients, roxadustat will be administered orally three times per week (TIW) and titrated to achieve the target response. It is expected that patients will require a higher dose due to bone marrow dysfunction and this is supported by experience with the earlier agent FG-2216 as discussed in [Section 2.4.2](#). The OL component will evaluate three cohorts (approximately 1.5 mg/kg, 2.0 mg/kg and 2.5 mg/kg) to optimize the starting dose for the DB component. After each 8 weeks on a dose level, the patient's response will be assessed and the study treatment will be titrated (pre-defined levels, [Appendix C](#)) to achieve transfusion independence. The study treatment can be down titrated at any time. Once the patient has achieved TI, the dose will be maintained as per [Appendix D](#). The regimen is consistent with that of the roxadustat CKD clinical development program and utilizes tiered body weight. The maximum permitted dose will be the same as that allowed in the CKD program of 400 mg or 3.5 mg/kg TIW (whichever is lower).

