### Appendix D - Dose Adjustment Rules for Patients who have TI for $\geq 56$ Days (8 weeks) – Maintenance Phase

A modified dose adjustment algorithm will apply to patients who have attained TI  $\geq 56$  days. The down titration of the dose is allowed at any time.

Change in Hb from 4 weeks earlier (g/dL)	Hemoglobin (Hb) Values			
	Hb <10.5 g/dL	Hb 10.5 to 12.9 g/dL	Hb >13.0 g/dL	Hb $\geq 13.5$ g/dL
< -1.0 * (or had RBC transfusion within 4 weeks)	↑	↑	No change	Hold, then resume dosing when: Hb <12 g/dL, at a dose that is reduced by one-dose level  Patients are to return weekly to monitor Hb until dosing can be resumed
-1.0 to 1.0	↑	No change	↓	
> 1.0	No change**	↓	↓	

\* A change in Hb from 4 weeks earlier of < -1.0 g/dL means a Hb value that is lower by more than 1.0 g/dL compared to 4 weeks earlier, e.g., a Hb of 9.4 g/dL compared to 10.6 g/dL 4 weeks earlier

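### Protocol Section 3.3.2 caps study-drug holds at one instance of two weeks, Appendix D requires an uncapped hold at Hb 13.5 g/dL or more, and no sentence reconciles the two

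*Protocol*

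**What the plan says.** Protocol Section 3.3.2 describes the correction and maintenance phases and then states a general limit: "Dosing with study medication may be held (not given) for one single instance not to exceed 2 weeks". The sentence is not tied to either phase or to any reason for holding. The next sentence sends questions to the medical monitor. Section 3.3.2 cites Appendix D only for moving the dose up or down, not for holds.

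Appendix D covers the maintenance phase: "A modified dose adjustment algorithm will apply to patients who have attained TI" for at least 56 days. In its column for Hb 13.5 g/dL or more the instruction is "Hold, then resume dosing when: Hb <12 g/dL, at a dose that is reduced by one-dose level", and "Patients are to return weekly to monitor Hb until dosing can be resumed". The hold ends on an Hb value. No maximum length and no maximum number of holds is given. SAP Section 19.1 reproduces the rule, also without a cap.

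Other parts of the protocol point maintenance dosing to Appendix D. In the Synopsis, once TI has lasted 8 weeks, "Maintenance Phase will begin and the study drug dose should follow guidance described in" that appendix. Section 2.5 says "Once the patient has achieved TI, the dose will be maintained as per" Appendix D, and Section 3.1 has similar wording. None of these mentions the limit in Section 3.3.2.

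Section 3.3.2 also contains a deviation waiver: "it is not considered a protocol deviation when study subjects are dosed based on their clinical circumstance". It excludes matters related to excessive hematopoiesis or overdose.

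**The concern.** Both rules apply to a maintenance-phase patient whose Hb reaches 13.5 g/dL, and in two situations they give incompatible instructions.

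1. Hb is still 12 g/dL or above at day 14 of the hold. The permission in Section 3.3.2 has run out, but the Appendix D condition for restarting is not met.
2. Hb reaches 13.5 g/dL again after one hold has been used. Appendix D requires a second hold, and Section 3.3.2 allows only one.

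What is at stake is safety. The Appendix D hold is the protocol's own response to overshoot on an erythropoietic drug. Section 2.6 relies on the dose algorithm to contain that risk, and the SAP lists deep vein thrombosis and pulmonary embolism among its events of special interest. About 80 planned sites should not each have to work out which rule prevails.

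**Working it through.** The plan states no figure on this point, so the check sets the rules side by side and then asks when both can be met.

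| | Section 3.3.2 | Appendix D, Hb 13.5 or more |
|---|---|---|
| Form | permission to hold | instruction to hold |
| Length | at most 2 weeks | until Hb is below 12 g/dL |
| Number | one | no limit |
| Scope | no phase or reason named | TI of at least 56 days |
| Mentions the other rule on holds | no | no |

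**Situation 1.** To satisfy both rules, Hb must be below 12 at day 14. The required fall per week is more than (starting Hb − 12) / 2.

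- From 13.5: (13.5 − 12) / 2 = 0.75, so more than 0.75 g/dL per week.
- From 14.0: (14.0 − 12) / 2 = 1.0, so more than 1.0 g/dL per week.

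The documents give no rate of fall off drug, so the rates below are assumptions. Day-14 Hb is the starting Hb − 2 × rate. Under Appendix D, dosing restarts at the first weekly check n for which starting Hb − rate × n is below 12.

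| Assumed fall (g/dL per week) | Day-14 Hb from 13.5 | First check below 12, from 13.5 | Weeks past the limit | First check below 12, from 14.0 |
|---|---|---|---|---|
| 0.25 | 13.0 | week 7 | 5 | week 9 |
| 0.5 | 12.5 | week 4 | 2 | week 5 |
| 0.75 | 12.0 | week 3 | 1 | week 3 |
| 1.0 | 11.5 | week 2 | 0 | week 3 |

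From 13.5 the rules are compatible only at the fastest of the four rates; from 14.0, at none of them. Therapeutic phlebotomy under Section 3.4.4 would shorten these times. The table shows when the rules diverge. It does not show how often they will.

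**Situation 2.** No rate is needed. A second Hb of 13.5 or more after one completed hold is enough.

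**The waiver.** It settles whether off-algorithm dosing counts as a deviation, not when drug may restart. Its exception concerns excessive hematopoiesis, which Appendix D describes as a rise of more than 2.0 g/dL within 4 weeks. For a patient at 13.5, that means Hb below 13.5 − 2.0 = 11.5 at any point in the preceding 4 weeks.

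**The primary endpoint.** Appendix D applies only after TI of at least 56 days. A patient who gets there within 28 weeks is already a responder; one who gets there later does so after the primary window has closed. A hold under Appendix D therefore cannot change primary response. The same reasoning covers the second test in the SAP sequence (TI of at least 56 days in 52 weeks), since the patient has already met it.

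**The case against.** The strongest reply is that the rules only appear to conflict. Section 3.3.2 is permissive and Appendix D is a specific, Hb-triggered instruction, and a specific instruction is normally read as prevailing over a general permission. The rest of the protocol supports this. Section 3.4.4 allows drug to be withheld for high Hb, and Appendix H allows dosing to resume after liver tests normalise. Neither sets a two-week cap, and both involve the medical monitor. With clinically driven interruptions uncapped in three places, Section 3.3.2 was probably written for discretionary holds.

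That stands as an account of what was probably intended. It does not supply the missing text: Section 3.3.2 does not confine itself to discretionary holds, and nothing in Appendix D, Section 3.4.4, Appendix H or the SAP sets its limit aside.

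A reader might go further and infer that Section 3.3.2 makes sites restart at day 14 with Hb at 12 or above, or dose through a second Hb of 13.5. The documents do not say so. Restarting, stopping and calling the medical monitor are all left open, and the only instruction given is to contact the monitor with questions. A site that restarted would also be overriding an explicit threshold in the table under which it sees the patient weekly.

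The mitigation argument also stands in part. Appendix C requires a dose reduction at Hb of 12 or more with TI of at least 56 days. Appendix D reduces the dose above 13.0 when Hb is stable or rising. The waiver may cover a site that holds past day 14, outside its exception. These make the conflict less likely to arise or to cause harm, but do not remove it.

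**Conclusion.** The point holds as a conflict between two stated rules. If Hb is still 12 g/dL or above at day 14 of an Appendix D hold, or returns to 13.5 after one hold, no course of action satisfies both. Appendix D is probably meant to govern, but a site has to infer it.

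The consequence is confined to dosing safety. The documents give neither the frequency of Hb 13.5 or more nor the rate of fall off drug. The number of patients affected is therefore unknown; that it is probably small is a judgment resting on the dose reductions required at lower Hb. Nobody should infer from this point that the primary result is at risk, and sample size, power and alpha are not involved.

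One further limit applies. The protocol reviewed is Amendment 02, whereas the SAP is based on Amendment 03 of 30 January 2020, which was not supplied and may already have resolved this. The change is worth considering, but the trial's validity does not depend on it.

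**What to change.** First check Amendment 03. If it does not already deal with this, add to Section 3.3.2: *This limit does not apply to holds required by Appendix D for Hb ≥13.5 g/dL, which continue until Hb <12 g/dL, or to safety interruptions under Section 3.4.4 or Appendix H.* Add a cross-reference to that sentence in the Hb 13.5 column of Appendix D.

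The cost is one sentence and one cross-reference. No visits are added, because Appendix D already requires weekly Hb checks during the hold. The SAP needs no change: Section 19.1 already carries the uncapped rule. SAP Section 17 reports that 140 patients have been enrolled in the double-blind component, so the benefit there is to patients still on drug.
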